5.4.1.3.3. Time to First Event Endpoint

For time to first event data, the hazard ratio will be estimated using the Cox proportional hazards model, adjusting for the baseline disease status (new-onset or relapsing GCA), and the baseline GC dose (≤ 30 mg/day or > 30 mg/day), and its associated 90% confidence interval will be presented. The proportional hazards assumption will be verified with appropriate methods (e.g. log-minus-log plots) as part of the analysis. The reported p-value for time to first flare analysis will be derived from a log-rank test. The survival curves will be estimated using Kaplan-Meier estimates.

Efficacy data through Week 28 and through Week 52 will be summarized and displayed by the following intervention groups:

1. Placebo
2. Guselkumab

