2.1.1. Unmet Need in Giant Cell Arteritis

Major unmet needs in GCA include non-invasive diagnostic tests, optimization of GC use to avoid GC related complications, identification of more targeted treatments, and identification of prognostic factors.

Despite an often-rapid improvement of symptoms following initial GC treatment, most patients develop serious adverse side effects related to long-term use of GCs, including GC-induced diabetes, arterial hypertension, osteoporosis, cataracts, infection, and psychosis (Baig 2019). In fact, an estimated 86% of patients treated with long-term GC therapy suffered from these GC-related complications within 10 years (Ness 2013).

Glucocorticoid tapering is typically started when symptomatology resolves and inflammatory markers normalize, with the goal to reduce the risks of long-term GC use. Tapering can result in either complete weaning off of GC or finding a low stable maintenance dose, however disease relapse is common (50% to 80%) during GC taper (Hachulla 2001; Weyand 2000). While the general view is that GC treatment can be reasonably stopped after 2 years, patients oftentimes require GC therapy for much longer (Hayreh 1997). Furthermore, a significant proportion (~25%) of patients do not achieve permanent remission (Proven 2003).

Due to the frequent complications of prolonged GC treatment, there is a need to develop GC-sparing maintenance therapies for GCA.

Tocilizumab (anti-IL6) is the only biologic approved for GCA. Its use is often limited to patients who fail GCs due to limited efficacy or safety concerns. Additionally, IL-6 receptor blockade with tocilizumab abrogates the hepatic synthesis of acute-phase reactants and renders CRP and ESR measurement unreliable for the purpose of monitoring disease activity in GCA in clinical practice (Prieto-González 2017).

Significant opportunity remains for the development of new treatment options for GCA that provide greater sustained GC-free remission with a favorable safety profile in newly diagnosed and relapsing GCA patients. A safe and efficacious alternative to GCs is an urgent unmet need in GCA and is a niche that guselkumab may fill given its well-characterized safety profile and durable responses in other indications where it has been shown to be effective.

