6.3. Measures to Minimize Bias: Randomization and Blinding

Intervention Allocation - Procedures for Randomization and Stratification

Central randomization will be implemented in this study. Participants will be randomly assigned to 1 of 2 intervention groups based on a computer-generated randomization schedule prepared before the study by or under the supervision of the sponsor. The randomization will be balanced by using randomly permuted blocks and will be stratified by new-onset and relapsing GCA and baseline GC use (≤ 30 mg/day or > 30 mg/day). The interactive web response system (IWRS) will assign a unique intervention code, which will dictate the intervention assignment and matching study intervention kit for the participant. The requestor must use his or her own user identification and personal identification number when contacting the IWRS and will then give the relevant participant details to uniquely identify the participant.

Blinding

To maintain the study blind, the study intervention container will have a label containing the study name, study intervention number, reference number, and storage conditions. The label will not identify the study intervention in the container. However, if it is necessary for a participant's safety, the study blind may be broken, and the identity of the study intervention ascertained. The study intervention number will be entered in the eCRF when the study intervention is administered. The study interventions will be identical in appearance and will be packaged in identical containers.

The investigator will not be provided with randomization codes. The codes will be maintained within the IWRS, which has the functionality to allow the investigator to break the blind for an individual participant.

Data that may potentially unblind the intervention assignment (ie, study intervention serum concentrations, anti-guselkumab antibodies, study intervention preparation/accountability data, intervention allocation, biomarker, or other specific laboratory data) will be handled with special care to ensure that the integrity of the blind is maintained and the potential for bias is minimized. This can include making special provisions, such as segregating the data in question from view by the investigators, clinical team, or others as appropriate until the time of DBL and unblinding.

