9.4.3. Secondary Endpoints

Secondary Endpoints:

- The proportion of participants achieving GC-free remission from Week 28 by visit through Week 52
- The proportion of participants achieving GC-free remission and normalization of ESR at Week 28 and by visit through Week 52
- The proportion of participants achieving GC-free remission and normalization of CRP at Week 28 and by visit through Week 52

- The proportion of participants achieving GC-free remission and normalization of both ESR and CRP at Week 28 and by visit through Week 52
- The cumulative GC dose through Week 28 and through Week 52
- The time to first GCA disease flare or discontinuation of study intervention due to AE of worsening of GCA through Week 28 and through Week 52
- The number of GCA disease flares or discontinuation of study intervention due to AE of worsening of GCA through Week 28 and through Week 52

Secondary Endpoint Analyses

The Full Analyses Set population will be used for analysis and participants will be counted in the intervention group assigned, regardless of the study intervention received.

The details of the analysis of the secondary endpoints will be included in the SAP.

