3. SAMPLE SIZE DETERMINATION

Approximately 51 participants are planned to be randomized into the study. The assumptions for the sample size and power calculation were based on the data from the Actemra Phase 3 GCA study. In the Actemra Phase 3 study, the proportions of participants in GC-free remission at Week 28 were estimated to be approximately 38% and 74% for placebo (+26-week GC taper) and Actemra qw (+26-week GC-taper), respectively, for a treatment difference of 36%.

Based on the data above, the GC-free remission rates at Week 28 are assumed to be 40% for placebo and 80% for guselkumab treatment arm. Based on these assumptions, 51 participants are planned to be randomized in a 2:1 ratio to either the guselkumab group (N=34) or the placebo

group (N=17). These sample sizes provide the study with 82% power to detect a difference in the primary endpoint between the 2 study intervention groups.

Table 1 shows the power to detect a difference in proportions of participants in GC-free remission between the guselkumab and placebo intervention groups at Week 28 under various assumptions.

Table 1: Power to Detect Difference in Proportions of Participants Achieving Glucocorticoid-free Remission between the Guselkumab and Placebo Intervention Groups at Week 28

Placebo (n = 17)	Guselkumab (n = 34)	Power (%)
35%	70%	68
	75%	81
	80%	90
40%	75%	69
	80%	82
	85%	91

Notes:

- The power calculation is based on two-sample Z test with continuity correction (pooled variance) under the normal distribution approximation.
- Power calculation is based on a 2-sided significance level of 0.10.
- Total sample size is 60.

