5.3.3. Analysis Methods for the Primary Estimand

The primary endpoint will be compared between the guselkumab group and the placebo group at Week 28 based on the primary estimand (Section 5.3.2.1) and the data from all participants in FAS (Section 4) will include data from all randomized participants who received at least one administration of study intervention based on their assigned intervention group, regardless of the actual intervention received.

The primary endpoint will be analyzed using the primary estimand. Participants with ICEs 1-3 before Week 28 will be considered as GC-free remission non-responders at Week 28. Participants with ICE 4, observed data after this ICE will be utilized in the analysis. For participants experiencing multiple ICEs, an ICEs 2 or 3 will override an ICE in category 4.

After accounting for the ICEs for the primary estimand, the remaining missing data of the primary endpoint at Week 28 will be considered as a non-responder.

In this primary analysis, the proportion of participants who achieve GC-free remission at Week 28 will be summarized for each intervention group. To address the primary objective, Cochran-Mantel-Haenszel chi-square statistic stratified by baseline disease status (new-onset and relapsing GCA), and the baseline GC dose (≤ 30 mg/day or > 30 mg/day) at a 2-sided significance level of 0.10 will be used. Difference in response rates between the guselkumab group and the placebo group at Week 28 adjusted for baseline disease status (new-onset and relapsing GCA), and the baseline GC dose (≤ 30 mg/day or > 30 mg/day) using Mantel-Haenszel weight and the corresponding 90% CI will be presented. Baseline disease status (new-onset and relapsing GCA), and the baseline GC dose (≤ 30 mg/day or > 30 mg/day) entered into IWRS are to be used. Similar analyses using the observed baseline disease status (new-onset and relapsing GCA), and the observed baseline GC dose (≤ 30 mg/day or > 30 mg/day) will be performed as sensitivity analyses.

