Sec 4	Binary response variable, where a responder is defined as a participant achieving GC-free remission and normalization of both ESR and CRP at Week 28 and from Week 28 through Week 52 by visit	Difference in the proportion of achieving GC-free remission and normalization of both ESR and CRP between the guselkumab group and the placebo group	
 1. The analysis strategies for the Week 28 endpoint will be the same as those for the primary estimand. 2. The analysis strategies for summary over time by visit from Week 28 through Week 52 are the same as those in #1 in this table.
Sec 5	Cumulative GC dose through Week 28 and through Week 52	Descriptive statistics for the guselkumab group and the placebo group	Treatment Policy strategy will be used regardless of the ICEs.
Sec 6	Time to first GCA disease flare or discontinuation of study intervention due to AE of worsening of GCA through Week 28 and through Week 52	Hazard ratio of the guselkumab group vs. the placebo group	Treatment Policy strategy will be used regardless of the ICEs.
Sec 7	Number of GCA disease flares or discontinuation of study intervention due to AE of worsening of GCA through Week 28 and through Week 52	Descriptive statistics for the guselkumab group and the placebo group	Treatment Policy strategy will be used regardless of the ICEs.

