5.4.1.3.2. Continuous Endpoint (Secondary Endpoints 5, 7)

Analyses for continuous endpoints will be based upon the Treatment Policy estimand. If a participant experiences an intercurrent event, the intercurrent event does not affect the outcome, and the data collected at and after the event will be used for analysis. Missing data will not be imputed.

The total cumulative glucocorticoid dose will be compared between the guselkumab and the placebo groups using van Elteren test stratified by baseline disease status (new-onset and relapsing GCA) and baseline GC dose (≤ 30 mg/day or > 30 mg/day) at Week 28.

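### The time-to-first-flare p-value comes from a log-rank test with no strata named, while the hazard ratio beside it is adjusted for both randomisation factors

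*SAP*

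**What the plan says.** For time to first flare or discontinuation for worsening GCA, SAP 5.4.1.3.3 fits a Cox model with baseline disease status and baseline GC dose as covariates and reports the hazard ratio with a 90% CI. The p-value comes from elsewhere: "The reported p-value for time to first flare analysis will be derived from a log-rank test". Kaplan-Meier curves follow. SAP Table 2 (5.4.1.2) gives the summary measure as "Hazard ratio of the guselkumab group vs. the placebo group".

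The same two factors define the randomisation, which under Protocol 6.3 "will be stratified by new-onset and relapsing GCA and baseline GC use". The SAP repeats them for its other comparative tests: CMH for the primary endpoint (5.3.3) and binary secondary endpoints (5.4.1.3.1), and for cumulative GC dose a comparison "using van Elteren test stratified by baseline disease status" and GC dose (5.4.1.3.2). For the primary analysis, 5.3.3 adds that the stratum values "entered into IWRS are to be used".

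Nothing else fills the gap. SAP 5.1 has no general stratification rule, and Protocol 9.4.1 mentions only Kaplan-Meier and Cox for time-to-event data. Using a log-rank test is within the SAP's remit, since Protocol 9.4.3 states: "The details of the analysis of the secondary endpoints will be included in the SAP".

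**The concern.** Randomising within strata balances the arms on the two factors, so the between-arm comparison varies less from trial to trial than under simple randomisation. An unstratified log-rank test still uses a variance that ignores this. If the factors predict flare, the test rejects too rarely.

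Two practical consequences follow. The p-value and the adjusted interval come from different models and can give different answers at the 0.10 level. Also, two programmers could read the sentence differently and produce two p-values. What is at stake is limited to the nominal p-value of one secondary endpoint; the adjusted hazard ratio and its 90% CI are reported either way.

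**Working it through.** **1. Tests side by side.**

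| Endpoint | Method | Randomisation factors named |
|---|---|---|
| Primary; secondary 1-4 | CMH | both |
| Secondary 5, cumulative GC dose | van Elteren | both |
| Secondary 6, hazard ratio | Cox | both |
| Secondary 6, p-value | log-rank | none |
| Secondary 7, number of flares | descriptive only | not applicable |

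**2. The plan's own figure.** The documents give no power or event count for flare, only 82% for the primary endpoint (40% vs 80%, 17 vs 34, two-sided 0.10, pooled variance, continuity correction). Pooled p = (17×0.4 + 34×0.8)/51 = 0.667. Null SE = √(0.667×0.333×(1/17+1/34)) = 0.140. Alternative SE = √(0.24/17 + 0.16/34) = 0.137. Correction = 0.5×(1/17+1/34) = 0.044. Power = Φ((0.40 − 0.044 − 1.645×0.140)/0.137) = 82%, as stated.

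**3. Inputs for the flare simulation.** From the documents: N = 51, 2:1, two-sided 0.10, permuted blocks in four strata, 70% relapsing (the preferential limit). The sample-size section says that "the GC-free remission rates at Week 28 are assumed to be 40% for placebo and 80% for guselkumab treatment arm". That gives 60% vs 20% events by Week 28, an upper bound for flare because non-remission has other causes too. Protocol 2.1.1 says "disease relapse is common (50% to 80%) during GC taper", which supports the Week 28 rate only.

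Assumed, not in the documents: block size 3, 50% of participants above 30 mg/day, exponential times, a hazard ratio of 1, 1.5, 2 or 3 for each factor, and a half-effect scenario of 60% vs 40%.

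With no prognostic effect, the treatment hazard ratio is ln(0.8)/ln(0.4) = 0.244 (planned) or ln(0.6)/ln(0.4) = 0.557 (half). It was recalibrated to the same Week 28 rates for the other factor strengths. A constant hazard implies 1 − 0.4^(52/28) = 82% placebo events by Week 52, which is an extrapolation.

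**4. Statistic.** Z = Σ(g − p)/√Σp(1 − p) over events, where g is 1 for a guselkumab event and p is the guselkumab share of those at risk. Risk sets are pooled (unstratified) or formed within the four strata (stratified). Disagreement means that the test and the adjusted Cox 90% CI differ on significance at 0.10.

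**5. Results**, unstratified / stratified, %, 20,000 trials per cell (Monte Carlo SE about 0.2 points for type I error, at most 0.35 for power):

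| Factor HR (each) | 1 | 1.5 | 2 | 3 |
|---|---|---|---|---|
| Type I, Week 28 | 10.2 / 10.2 | 9.5 / 10.2 | 8.5 / 10.6 | 6.2 / 10.4 |
| Type I, Week 52 | 10.3 / 10.4 | 9.7 / 10.5 | 8.2 / 10.9 | 5.9 / 10.6 |
| Power, planned, Week 28 | 90.8 / 90.0 | 90.9 / 90.8 | 91.3 / 92.2 | 92.9 / 95.2 |
| Power, planned, Week 52 | 97.8 / 97.4 | 97.7 / 97.7 | 97.4 / 98.0 | 97.2 / 98.8 |
| Power, half, Week 28 | 42.7 / 41.4 | 42.2 / 42.7 | 41.9 / 45.1 | 42.4 / 51.5 |
| Power, half, Week 52 | 52.8 / 50.6 | 51.7 / 52.0 | 49.6 / 54.5 | 47.6 / 60.4 |
| Disagreement, planned, Week 28 | 1.5 / 1.7 | 1.7 / 1.4 | 2.1 / 1.2 | 3.0 / 0.9 |
| Disagreement, planned, Week 52 | 0.4 / 0.7 | 0.7 / 0.7 | 1.1 / 0.5 | 1.9 / 0.3 |
| Disagreement, half, Week 28 | 3.6 / 4.4 | 4.4 / 4.3 | 7.2 / 4.1 | 12.6 / 4.7 |
| Disagreement, half, Week 52 | 4.3 / 6.8 | 6.6 / 6.1 | 10.6 / 6.2 | 17.8 / 6.1 |

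**6. Direction.** At half effect, Week 52, the unstratified test gives p > 0.10 beside a CI excluding 1 in 2.3/4.6/8.9/16.4% of trials across the four factor strengths. The reverse occurs in 2.0/2.0/1.7/1.4%.

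**7. Sensitivity.**
- One factor only, HR 2: at half effect, Week 52, power is 51.5 vs 52.7% (relapsing) or 51.0 vs 52.8% (GC dose).
- Week 52 with the hazard halved after Week 28 and 15% dropout, factor HR 3: power is 95.4 vs 97.3% (planned) and 44.4 vs 55.2% (half).
- A second simulation (8,000 trials, 60% placebo events only by Week 52, 60% relapsing): type I error is 8.6, 5.9 and 3.9% unstratified at factor HR 2, 3 and 5, against 10.8, 11.0 and 11.1% stratified. At treatment HR 0.244, power is 88 vs 92% for factor HR 3 and 81 vs 93% for factor HR 5. At treatment HR 0.40 it is 59 vs 68% and 48 vs 70%.

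**The case against.** The strongest reply is that this is silence, not error. An unstratified log-rank test is valid, and its simulated type I error in the main runs never exceeds 10.3%. It also matches the Kaplan-Meier curves, which are planned by arm with no strata. With 17 placebo participants in four strata (about 17×0.7×0.5 = 6 in each relapsing cell and 17×0.3×0.5 = 2.5 in each new-onset cell), sparse strata could be a deliberate reason not to stratify. If the factors are not prognostic, stratifying loses 0.4 to 2.2 points of power and raises disagreement with the CI (half effect, Week 52: 4.3 to 6.8%). The taper table in Protocol 10.8 gives some reason to doubt that baseline dose matters, because its four columns are identical from Week 8 on. The explicit stratified precedents (CMH, van Elteren) are written for Week 28, not Week 52. And 5.4.1.3.3 does not say whether the Cox model uses IWRS or observed values.

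All of this stands, and it sets the priority low. It does not remove the gap. The SAP accepts the same four strata for its other tests and gives no reason for treating this one differently. The last point belongs in the fix.

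**Conclusion.** The concern holds as a cheap, low-priority improvement. Leaving out the strata does not inflate type I error; it makes the test conservative to a degree set by prognostic strength, which neither document gives. In the main runs the largest power difference at the planned effect is 95.2 − 92.9 = 2.3 points. At half effect and factor HR 3 it is 51.5 − 42.4 = 9.1 points (Week 28) and 60.4 − 47.6 = 12.8 points (Week 52). With fewer events by Week 52 the cost at factor HR 3 is about 4 points at the planned treatment hazard ratio. Only factors stronger than HR 3 make it large there. With weak factors (HR 1 to 1.5) the two tests are practically equivalent. These sizes rest on the assumed stratum mix, block size, exponential times and event rates.

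**What to change.** In SAP 5.4.1.3.3, specify a log-rank test stratified by baseline disease status and baseline GC dose for both Week 28 and Week 52. State in the same place that this test and the Cox model both use the IWRS values, so that the p-value and the interval rest on the same stratum data. If an unstratified test is intended because of sparse strata or to match the Kaplan-Meier curves, say so there. Settle the wording before the Week 28 database lock, when limited sponsor personnel are unblinded.

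The change costs one sentence and one programming option. Its statistical price is the small power loss noted above if the factors are not prognostic, and a type I error of about 10 to 11%. Some disagreement between p-value and CI will remain, because a score test and a Wald interval differ; the adjusted Cox Wald test itself runs at 10.6 to 10.9% (Week 28) and 11.0 to 11.6% (Week 52).

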5.5. Exploratory Endpoints Analysis for the Main Study

Objective: To evaluate the efficacy of guselkumab with a compared to placebo, in combination with a 26-week GC taper regimen, in adult participants with new-onset or relapsing GCA for the following exploratory endpoints:

Other Efficacy Endpoints

- Summary of signs, symptoms, and elevated CRP and/or ESR due to GCA disease flares
- Proportion of participants who experience at least one GCA disease flare or discontinuation of study intervention due to AE of worsening of GCA through week 28 and from Week 28 through Week 52 by visit
- Proportion of participants in sustained remission through Week 52 following remission at Week 8
- Proportion of participants in sustained remission through Week 52 following remission at Week 12
- Proportion of participants in sustained remission through Week 52 following remission at Week 16
- Proportion of participants in sustained remission from Week 28 through Week 52 by visit following remission at Week 8
- Proportion of participants in sustained remission from Week 28 through Week 52 by visit following remission at Week 12
- Proportion of participants in sustained remission from Week 28 through Week 52 by visit following remission at Week 16
- Cumulative GC dose through Week 28 and through Week 52 by baseline disease status (new-onset or relapsing GCA)
- Cumulative GC dose through Week 28 and through Week 52 by baseline GC dose (≤ 30 mg/day or > 30 mg/day)
- Change from baseline in ESR through Week 28 and from Week 28 through Week 52 by visit
- Proportion of participants with normalization of ESR through Week 28 and from Week 28 through Week 52 by visit
- Change from baseline in CRP through Week 28 and from Week 28 through Week 52 by visit
- Proportion of participants with normalization of CRP through Week 28 and from Week 28 through Week 52 by visit

Sustained remission through Week 52 is defined as: No signs and symptoms of GCA through Week 52, and completion of the protocol defined GC taper, and not having required GC rescue therapy at any time by Week 52.

Efficacy data through Week 28 and through Week 52 will be summarized and displayed by the following intervention groups:

1. Placebo
2. Guselkumab

Clinical Outcome Assessments (COAs)

In this study, patient-reported outcome measures include patient's global assessment of their GCA disease activity (PGA), pain severity assessment, SF-36 health survey, Functional Assessment of Chronic Illness Therapy-Fatigue (FACIT-fatigue) and a clinician-reported outcome, the Physician's Global Assessment of Disease Activity (PhGA). The following analyses will be performed by treatment group. This section outlines the definitions and analyses for the following PRO and ClinRO endpoints.

Other efficacy endpoints related to COAs include:

Patient-reported Outcomes

- Change from baseline in PGA at Week 28 and at Week 52.
- Change from baseline in Pain Severity Assessment at Week 28 and at Week 52.
- Change from baseline SF-36 PCS (physical component summary) score and MCS (mental component summary) score at Week 28 and at Week 52.
- Change from baseline in SF-36 individual domains at Week 28 and at Week 52.
- Change from baseline in FACIT-fatigue scale score (raw score) at Week 28 and Week 52.
- Proportions of participants with FACIT-fatigue scale score ≥ 40 (mean=40, SD=10) at Week 0, 28, and 52.
- Proportions of participants with ≥ 4 -points improvement in FACIT-fatigue scale score (raw score) at Week 28 and 52.

Physician-reported Outcomes

- Change from baseline in PhGA at Week 28 and Week 52.

COAs data at Week 28 and Week 52 will be summarized and displayed by the following intervention groups:

1. Placebo
2. Guselkumab

5.5.1. Definition of Endpoints**5.5.1.1. Sustained Remission through Week 52 Following Induction of Remission at Week 8**

1. Remission at Week 8
AND
2. No signs or symptoms of active GCA from Week 8 through Week 52, inclusive
AND
3. Adherence to the protocol specified 26-week GC taper
AND
4. Absence of GCA flare from first dose through Week 52

Similar definitions for sustained remission through Week 52 following induction of remission at Week 12 and following induction of remission at Week 16.

5.5.1.2. Sustained Remission from Week 28 through Week 52 by Visit Following Induction of Remission at Week 8

1. Remission at Week 8
AND
2. No signs or symptoms of active GCA from Week 8 through Week X, inclusive
AND
3. Adherence to the protocol specified 26-week GC taper
AND
4. Absence of GCA flare from first dose through Week X

Similar definitions for sustained remission through Week X following induction of remission at Week 12 and following induction of remission at Week 16.

